1.2. Rationale for the study

Because the infectious aetiology of AECOPD has been suggested to vary according to geographical region, the primary purpose of this study (which will be conducted in several countries in Asia Pacific) is to evaluate the occurrence of potential bacterial and viral pathogens in the sputum of stable COPD patients and at the time of AECOPD. Given the increasing and projected burden of COPD in the Asia Pacific region, this study will also evaluate the frequency, severity and duration of AECOPD, as well as the impact of AECOPD on health-related quality of life (HRQOL), healthcare utilisation and lung function.

In addition, both PCR and bacteriological methods will be used for characterisation and (quantification in some cases) of bacteria in sputum. To date, identification of bacteria and assessment of bacterial load is done in the vast majority of cases by culture. However, the few studies that have compared culture with PCR demonstrated that PCR is more discriminatory at detecting typical airway bacteria [Curran, 2007; Singh, 2014]. Moreover, in a multi-centre study, PCR has the advantage that it can be performed on stored sputum samples, and can therefore be done centrally, whereas culture has to be performed on fresh sputum samples, which can lead to variable results due to variability in testing methods between laboratories.

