Objectives	
Primary
 
To estimate the proportion of potential bacterial and viral pathogens (overall and by species) detected in sputum of stable COPD patients and during AECOPD, using respectively bacteriological methods and viral PCR, over the course of 1 year.
 
Secondary
 
• To evaluate the concordance between PCR and bacteriological methods data in sputum for potential bacterial pathogens.• To estimate the proportion of potential bacterial and viral pathogens (overall and by species) detected in sputum of stable COPD patients, by GOLD grade.• To estimate the proportion of potential bacterial and viral pathogens (overall and by species) detected in sputum during AECOPD, by severity of AECOPD.• To estimate the incidence rate of all-cause AECOPD, overall and by GOLD grade.• To describe the severity and duration of all-cause AECOPD, overall and by GOLD grade.• To assess the impact of all-cause AECOPD on HRQOL.• To assess the impact of all-cause AECOPD on lung function.• To assess the impact of all-cause AECOPD on healthcare utilisation.

Tertiary

- To assess the use of EXACT-PRO for determining the end date of AECOPD.
- To evaluate the load of bacterial and viral pathogens in stable COPD and during AECOPD.
- To collect biological specimens for future respiratory disease-related testing:
 - Aliquots of sputum samples for assay development and microbiome analysis at stable visits and during exacerbation.
 - Blood sampling for potential identification/quantification of biomarkers at Visit 1 and Visit 3.

Rationale for the study

Because the infectious aetiology of AECOPD has been suggested to vary according to geographical region, the primary purpose of this study (which will be conducted in several countries in Asia Pacific) is to evaluate the occurrence of potential bacterial and viral pathogens in the sputum of stable COPD patients and at the time of AECOPD. Given the increasing and projected burden of COPD in the Asia Pacific region, this study will also evaluate the frequency, severity and duration of AECOPD, as well as the impact of AECOPD on health-related quality of life (HRQOL), healthcare utilisation and lung function.

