4.1.1. Recruitment of study centres

Centres will be selected for study participation based on the following criteria:

- Experience with patients with respiratory disorders.
- Able to perform microbiology testing. Please refer to SPM for details on the requirements to be met for microbiology testing.
- No limitations on the quantity of export of biological samples to GSK Biologicals or to designated laboratories.

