6.5.3. Laboratory assays (Amended 19 October 2018)

Please refer to [APPENDIX A](#) for the address of the clinical laboratories used for sample analysis.

The quality of sputum samples will be assessed at the investigator's institution and/ or at a laboratory designated by GSK Biologicals by gram staining.

Standard bacteriological methods (and semi-quantitative counts) will be performed on fresh sputum samples at the investigator's institution and/or at a laboratory designated by GSK Biologicals. Identification of potential bacterial pathogens will be performed according to agreed identification methods (potential pathogens including, but not necessarily limited to, *H. influenzae*, *S. pneumoniae*, *M. catarrhalis*, *S. aureus*, *P. aeruginosa*, *K. pneumoniae* and *A. baumannii*). All results should be entered in the eCRF.

Further bacterial characterization for *H. influenzae* isolates: Identified *H. influenzae* isolates should be collected and stored in the investigator's institution and will undergo further species confirmation (i.e. confirmed *H. influenzae*) and when possible, further differentiation (i.e., Hi/NTHi) at GSK Biologicals' laboratory or at a laboratory designated by GSK Biologicals using molecular techniques such as PCR. Identified *H. influenzae* isolates might undergo further testing at GSK Biologicals' laboratory or at a laboratory designated by GSK Biologicals' using other molecular techniques such as PCR and sequencing.

Identified *M. catarrhalis* isolates should be collected and stored in the investigator's institution and might undergo further species confirmation (and when possible, further differentiation) at GSK Biologicals' laboratory or at a laboratory designated by GSK Biologicals using molecular techniques such as PCR and sequencing.

Identified *P. aeruginosa* isolates should be collected and stored in the investigator's institution and might potentially undergo further testing at GSK Biologicals' laboratory or at a laboratory designated by GSK Biologicals.

Further bacterial pathogens identification (including, but not necessarily limited to, *H. influenzae*, *S. pneumoniae*, *M. catarrhalis*, *S. pyogenes*, *S. aureus* and *P. aeruginosa*) and quantification (for *H. influenzae*, *S. pneumoniae*, *M. catarrhalis*) on stored sputum samples will be performed at GSK Biologicals' laboratory or a laboratory designated by GSK Biologicals using qualitative PCR and/or quantitative PCR.

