6.2. Analysis of primary objective

The analysis of the primary objective will be performed on the FAS.

Average proportion of patients with sputum samples positive for bacterial or viral pathogens overall and for specific species, and its exact 95% confidence interval (CIs) will be computed at any stable scheduled visit and at any exacerbation visit for the entire study period. In addition, the average proportion of sputum samples positive for bacterial and viral pathogens overall and for specific species, and its 95% confidence interval will also be computed at any stable scheduled visit and at any exacerbation visit for the entire study period. Confidence intervals will be estimated using a Generalized Estimating Equations (GEE) model assuming a binomial distribution for the response variable with logit as link function and a compound symmetry correlation matrix (exchangeable structure) to account for the within-patient correlations (Liang, 1986) (more details in section 6.2.1). If the GEE model will not run due to only one level of the outcome variable, the exact 95% confidence interval will be computed. Proportion of patients with sputum samples positive for bacterial/viral pathogens overall and for specific species, will be computed, with exact 95% CIs, at each stable* scheduled visit (visit 1, visit 2, visit3) and at each exacerbation visit confirming acute exacerbation**.***.

* A confirmed stable visit will be defined as a scheduled study visit for which the investigator confirms in the eCRF that the patient is stable/has recovered from a previous exacerbation.

** If an AECOPD occurs at the time when one of the scheduled [stable] study visits is planned, it should be handled and recorded as an AECOPD visit. If possible, the stable study visit should be re-scheduled to a later date, within the ± 14 days' time window from the scheduled appointment, when the patient is stable again.

*** The definition of acute exacerbation of COPD (AECOPD) event is detailed in section 12.

CONFIDENTIAL

201112 (EPI-NTHI-001 BOD APA)
 Statistical Analysis Plan Amendment 2 Final

In details the following pathogens will be evaluated:

- Bacteria including, but not necessarily limited to, *H. influenzae**, *M. catarrhalis*, *S. pneumoniae*, *S. aureus*, *P. aeruginosa*, *K. pneumoniae* and *A. baumannii* by bacteriological methods (culture).

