6.3.1. Concordance between molecular (PCR) and bacteriological methods

The frequency distribution of sputum samples positive or negative for specific bacterial species (including but not necessarily limited to *H. influenzae*, *M. catarrhalis*, *S. pneumoniae*, *S. aureus* and *P. aeruginosa*) obtained from PCR will be tabulated versus results obtained from culture at any visit (stable scheduled visits or AECOPD visits).

The concordance between culture and PCR, at any visit, will be evaluated using the Cohen's kappa (κ) statistic and 95% CI. Concordance will be interpreted as good (>0.79), substantial (0.60–0.79), moderate (0.40–0.59), fair (0.21–0.39) or no concordance (<0.21) (McHugh, 2012).

Proportion of patients with sputum samples positive for bacterial pathogens (including but not necessarily limited to *H. influenzae*, *M. catarrhalis*, *S. pneumoniae*, *S. aureus*, *P. aeruginosa*, *K. pneumoniae* and *A. baumannii*) by PCR will be computed, with 95% CIs, at each and any stable scheduled visit and at each and any AECOPD visit confirming acute exacerbation.

6.3.2. Proportion of potential bacterial/viral pathogens by country, GOLD grade and by AECOPD severity

Average proportion of patients with sputum samples positive for bacterial or viral pathogens overall and for specific species, will be computed, with 95% CIs, at any stable scheduled visit and at any AECOPD visit confirming acute exacerbation [mild, moderate, severe] by GOLD classification [GOLD 2, 3, 4].

Average proportion of patients with sputum samples positive for bacterial or viral pathogens overall and for specific species, will be computed, with 95% CIs, at any stable scheduled visit and at any AECOPD visit confirming acute exacerbation by country.

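### By-country bacterial detection appears to rest on culture, and no by-country PCR proportions or culture-PCR agreement are planned, so country cannot be told apart from laboratory

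*Protocol*

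**What the plan says.** The rationale opens with geography: "Because the infectious aetiology of AECOPD has been suggested to vary according to geographical region". The same section (Protocol 1.2) states that "culture has to be performed on fresh sputum samples, which can lead to variable results due to variability in testing methods between laboratories", and that "PCR has the advantage that it can be performed on stored sputum samples, and can therefore be done centrally".

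Protocol 6.5.3 says standard bacteriological methods "will be performed on fresh sputum samples at the investigator's institution and/or at a laboratory designated by GSK Biologicals". It also gives some standardisation: "Identification of potential bacterial pathogens will be performed according to agreed identification methods". Protocol 4.1.1 selects centres partly on microbiology capability, with the requirements in the study procedures manual.

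SAP 6.2 takes culture as the bacterial method for the primary objective. SAP 6.3.2 then gives the average proportion positive for bacteria or viruses "at any stable scheduled visit and at any AECOPD visit confirming acute exacerbation by country", and names no bacterial method. SAP 6.3.1 gives bacterial PCR proportions and Cohen's kappa between culture and PCR at stable and AECOPD visits, with no breakdown by country or laboratory. SAP 6.3.4.2 plans incidence of AECOPD with bacteria found by culture or by PCR, with country among the covariates. Protocol 9.6 plans similar rates (PCR, bacteriological methods, or both), also by country.

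**The concern.** The four places named in SAP section 2 (Hong Kong, Philippines, Korea, Taiwan) will have their own culture laboratories wherever culture is done at the investigator's institution. The rule that sputum be cultured within 6 hours of collection (Protocol 6.4.1.14, 6.4.2.15, 6.4.3.9) also favours testing close to the site. Laboratory is then largely nested within country, and observed culture positivity is prevalence multiplied by that laboratory's yield. A by-country table of culture results alone could show a regional difference where only laboratory practice differs, or hide a real one. The protocol names both the hazard and a less laboratory-dependent method, but the SAP text does not apply that method to the by-country detection proportions.

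**Working it through.** **1. The plan's own precision figure.** Protocol 9.2 expects about 140 AECOPD samples from 200 enrolled; 200 × 0.9 × 0.8 = 144, which is close. For 30% positive, the exact (Clopper-Pearson) 95% interval with 42 of 140 is [22.6 ; 38.3], as in Table 12. That interval is for the pooled cohort. An equal split over four countries (assumed) gives 140 / 4 = 35 samples each, and the same formula at 30% (10.5 of 35, not a whole count) gives [15.7 ; 47.8].

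**2. Which bacterial outputs are planned by country, and by which method.**
- Detection proportions, stable and AECOPD (SAP 6.3.2): by country; method not named, culture by reading with SAP 6.2.
- PCR detection proportions (SAP 6.3.1): not by country.
- Culture-PCR kappa (SAP 6.3.1): not by country or laboratory.
- Bacteria-associated AECOPD incidence (SAP 6.3.4.2, Protocol 9.6): by country, culture or PCR; unclear whether separate rates or a composite; exacerbations only.
- Conditional logistic model: Protocol 9.7 mentions country for culture and repeats the model for PCR; the current SAP 6.4.4 does not mention country.

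No item gives stable-state bacterial detection by PCR by country, and none gives culture yield by country.

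**3. Size of the bias.** With prevalence π and yield s (the share of PCR-positive samples that culture detects), and no culture positives among PCR negatives, observed culture positivity is π × s. For two countries with the same π the false gap is π × (s1 − s2). Neither π nor s is in the documents; these values are assumptions. At π = 40%:
- 80% v 70%: 32% v 28%, gap 4 points
- 75% v 60%: 30% v 24%, gap 6 points
- 75% v 45%: 30% v 18%, gap 12 points

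**4. Against sampling error.** Take n = 200 × 3 × 0.9 / 4 = 135 stable samples per country, treated as independent. For 30% v 18% the standard error is √(0.30 × 0.70 / 135 + 0.18 × 0.82 / 135) = 0.0515, so z = 0.12 / 0.0515 = 2.33 and a nominal 5% comparison would flag the gap 64% of the time. The 4- and 6-point gaps are flagged 11% and 20% of the time.

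Repeat samples from one patient are correlated. With an assumed within-patient correlation of 0.3 to 0.5, the design effect 1 + (3 − 1) × ρ is 1.6 to 2.0, and the 64% falls to about 45% to 38%. With 35 AECOPD samples per country the three figures are about 7%, 9% and 22%. The bias in the point estimate stays at 4 to 12 points whatever the sample size.

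**The case against.** The strongest reply has five parts.

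- **PCR by country exists.** A reader might infer that PCR is never broken down by country for bacteria. That is not so: SAP 6.3.4.2 and Protocol 9.6 plan such incidence rates. They do not settle the matter, because they omit the stable state, combine detection with exacerbation frequency, and may include culture in a composite.
- **Culture is not simply local.** A designated laboratory is allowed, identification methods are agreed, H. influenzae isolates get PCR confirmation, and elimination code 2120 (SAP 5.4.4) covers late cultures and identification errors. This stands as mitigation. It does not measure yield, and confirming isolates cannot recover organisms that culture missed. How far culture is harmonised depends on manuals outside these documents.
- **Country comparison is not an objective.** No primary or secondary objective compares the participating countries, the background's contrast is Europe and the USA against Asia, and all analyses are descriptive (SAP 7). This lowers the stakes, but a descriptive country table is biased in the same way.
- **The method in SAP 6.3.2 is inferred.** True. The subgroup proportions in Protocol 9.6 do not settle it, because they are by GOLD grade, AECOPD severity and prior antibiotics, not by country. Culture is the likelier reading from SAP 6.2.
- **PCR is not truth.** Delayed freezing and temperature deviations (SAP 5.4.4) can affect PCR samples, and the quantitative cut-offs are set only at data release (SAP 11.2.4). This stands, and is why PCR belongs beside culture rather than in place of it.

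The table list and mock tables are in separate documents, so only the SAP text can be called silent.

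**Conclusion.** As the SAP is written, the by-country detection proportions cannot separate prevalence from culture yield. The bias is of unknown size; 4 to 12 points is an illustration resting on assumed yields and 40% prevalence. A reader might infer that a false country difference would probably reach nominal significance. The documents do not support that: no such test is planned, and the 64% needs the most extreme assumed yields and independent repeat samples. The point therefore rests on bias in the estimates, concerns the by-country outputs only, and is a worthwhile, inexpensive improvement.

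One limit remains. The PCR assays in SAP 11.2.4 do not target K. pneumoniae or A. baumannii, which Protocol 1.1 singles out for Asia. SAP 6.3.1 lists both for PCR proportions, and Protocol 6.5.3 makes their PCR only possible additional testing. Unless it is run, by-country results for these two species cannot be checked against PCR.

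**What to change.** - In SAP 6.3.2, name culture as the bacterial method and add PCR proportions by country, stable and AECOPD, for H. influenzae, M. catarrhalis, S. pneumoniae, S. aureus and P. aeruginosa.
- Show culture-PCR agreement by country, and by testing laboratory where recorded: the share of PCR-positive samples that are culture-positive, and kappa.
- In SAP 6.3.4.2, state that by-country incidence is given separately for culture and for PCR.
- Interpret country differences only where culture and PCR agree.
- Label by-country K. pneumoniae and A. baumannii results as culture-only and not separable from laboratory unless the optional PCR is run, and reconcile SAP 6.3.1 with 11.2.4.

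The cost is SAP wording and a few tables from data already planned for collection. Two species may stay culture-only, and PCR keeps its own exposure to site handling.

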2. OBJECTIVES

2.1. Primary objective

- To estimate the proportion of potential bacterial and viral pathogens (overall and by species) detected in sputum of stable COPD patients and during AECOPD, using respectively bacteriological methods and viral PCR, over the course of 1 year.

Refer to Section 9.1.1 for the definition of the primary endpoint.

2.2. Secondary objectives

- To evaluate the concordance between PCR and bacteriological methods data in sputum for potential bacterial pathogens.
- To estimate the proportion of potential bacterial and viral pathogens (overall and by species) detected in sputum of stable COPD patients, by GOLD grade.
- To estimate the proportion of potential bacterial and viral pathogens (overall and by species) detected in sputum during AECOPD, by severity of AECOPD.
- To estimate the incidence rate of all-cause AECOPD, overall and by GOLD grade.

- To describe the severity and duration of all-cause AECOPD, overall and by GOLD grade.
- To assess the impact of all-cause AECOPD on HRQOL.
- To assess the impact of all-cause AECOPD on lung function.
- To assess the impact of all-cause AECOPD on healthcare utilisation.

Refer to Section [9.1.2](#) for the definition of the secondary endpoints.

2.3. Tertiary objective(s)

- To assess the use of EXACT-PRO for determining the end date of AECOPD.
- To evaluate the load of bacterial and viral pathogen in stable COPD and during AECOPD.
- To collect biological specimens for future respiratory disease-related testing:
 - Aliquots of sputum samples for assay development and microbiome analysis at stable visits and during exacerbation.
 - Blood sampling for potential identification/quantification of biomarkers at Visit 1 and Visit 3.
 - Bacterial isolates for further strain characterisation.

[figure not shown]
Refer to Section [9.1.3](#) for the definition of the tertiary endpoints.

3. STUDY DESIGN OVERVIEW

Protocol waivers or exemptions are not allowed unless necessary for the management of immediate safety concerns. Therefore, adherence to the study design requirements, including those specified in the outline of study procedures (Section 6), are essential and required for study conduct.

Figure 2 presents an overview of the study design.

Figure 2 Study design overview

V = Visit; M = Month; SP = sputum sample; e-DC: Training and use of electronic Diary card; CAT = COPD assessment test; SGRQ-C = St. George's Respiratory Questionnaire for COPD patients; spiro = spirometry;

BS = Blood Sampling; AECOPD = acute exacerbation of COPD; ATS-DLD-078 = American Thoracic Society and National Heart and Lung Institute-Division of Lung Disease Respiratory Questionnaire

* The sputum samples during AECOPD should preferably be obtained before administration of the first dose of antibiotics to treat the AECOPD (if applicable). Self collection of the sputum sample will be allowed in specific cases, where the first dose of antibiotics absolutely needs to be taken before an AECOPD visit can take place.

This is not allowed at scheduled visits when subject should be in stable condition.

** Follow-up phone calls will take place at least every 2 weeks, until the AECOPD has resolved

Type of design: Prospective, epidemiological, interventional, multi-country, cohort study.

- Study population: A cohort of approximately 200 moderate to very severe COPD patients with at least 1 documented moderate or severe AECOPD in the year before enrolment.
- Type of study: self-contained.
- Data collection: Electronic Case Report Form (eCRF) and electronic diary cards.
- Primary completion Date: Visit 3 (Month 12). Refer to [glossary of terms](#) for the definition of PCD.
- End of Study (EoS): Last testing results released of samples collected at Visit 3.
- Duration of the study: The study will last approximately 1 year for each subject from screening visit up to study conclusion.

Note: Screening visit should ideally occur not more than 6 weeks before visit 1.

- **Epoch 001:** Prospective data collection starting at Screening Visit (Pre-month 0) and ending at Visit 3 (Month 12).

Table 3 Study groups and epochs foreseen in the study

Study Groups	Number of subjects	Age	Epoch
			Epoch 001
Prospective	Approx 200	≥ 40 years	X

- **Study visits/contacts:**
 - Screening visit.
 - Three scheduled (stable) study visits occurring at 6 months intervals.
 - For each AECOPD: AECOPD visit (within 96 hours of the onset of the symptoms) and follow-up phone call(s) (at least every 2 weeks until the AECOPD has resolved). Follow-up phone contacts will define end of AECOPD.
- **COPD symptoms**
Subjects will be asked to record their COPD symptoms in an electronic Diary Card on a daily basis:
 - Daily in the morning throughout the study: Morning symptoms questionnaire.
 - Daily at bedtime throughout the study: EXACT-PRO (EXAcerbations of Chronic Pulmonary Disease Tool - Patient Reported Outcome) questionnaire.
- **Biological samples:**
 - **Sputum samples** collected at site (spontaneous or induced, as per investigator judgement) will be collected at each study visit at the site (scheduled [stable] visits and AECOPD visits) if, in the opinion of the investigator, it is safe for the subject.

Or

- **Sputum sample collected at subject's home (spontaneous).** Self-collection of the sputum sample will be allowed in specific cases, where the first dose of antibiotics absolutely needs to be taken before an AECOPD visit can take place. This is not allowed at scheduled visits when subject should be in stable condition.

Note: The sputum samples collected during AECOPD should preferably be obtained before administration of the first dose of antibiotics to treat the AECOPD (if applicable).

- **Blood samples** for biomarker testing will be collected at Visit 1 (M0) and Visit 3 (M12).

- **HRQOL assessments**

- Subjects will be asked to complete the COPD assessment Test (*CAT*) at each study visit (scheduled [stable] visits and AECOPD visits).
- Subjects will be asked to complete the St. George's Respiratory Questionnaire for COPD patients (SGRQ-C) at each scheduled (stable) study visit (Visit 1 [Month 0], Visit 2 [Month 6] and at Visit 3 [Month 12]).
- Pre- and post-bronchodilator spirometry assessments will be done for all subjects at Screening Visit (pre-Month 0) and at Visit 3 (Month 12).

